1 SYNOPSIS

TITLE: Rapid HCV Test and Treat to increase HCV treatment among people who use drugs (RAPID-HCV)

DESIGN: Open label multicenter, phase IV randomized trial of a test and treat strategy with peer enhancement for HCV treatment at drug treatment programs versus standard of care referral for HCV treatment.

DURATION: Participants will be on study for up to a total of 12 months after HCV treatment initiation (treatment and observation period).

SAMPLE SIZE: 124 HCV infected participants will be enrolled in the study from five drug treatment programs in four cities (Baltimore Maryland, Birmingham Alabama, San Francisco California and Toronto Canada). Up to 15 peers and 45 drug treatment program staff members (for in-depth interviews only) will be enrolled across all sites. Total enrollment up to 184 participants.

POPULATION: People who use drugs enrolled in drug treatment programs with confirmed ongoing HCV infection.

All participants ≥ 18 years of age enrolled at study drug treatment sites who have ongoing HCV infection (as determined through study testing procedures).

STUDY DRUG AND DURATION OF TREATMENT: Subjects will receive GLE/PIB fixed-dose combination (300 mg/120 mg) QD for 8 weeks.

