The peer will contact the patient 2 days before and the day before the scheduled appointment to remind that participant about the appointment.

Peers will have a standard protocol for at least weekly phone contact with participants through post-treatment week 12, and will be available to answer participant questions as needed. Peers will maintain a log of peer contact, which will be submitted to research program staff weekly.

Peers will have access to drug treatment clinic staff for support with trouble shooting any arising matters.

Peers will submit weekly logs of participant contact to the research program coordinator and meet as a group (both peers and research program coordinator at each site, either virtually or in person) to review best practices and address any issues or questions related to effective performance as a peer.

If the participant does not want to work with the assigned peer, they can choose not to receive peer services.

HCV treatment initiation. At the treatment initiation visit, if still eligible for the study after all Day 0 results are available (detectable HCV RNA, platelet count >150,000, not pregnant) the patient will be offered immediate initiation of HCV treatment.

HCV treatment will be initiated at the drug treatment center. Participants will be provided a 4-week supply of glecaprevir/pibrentasvir (GLE/PIB) combination. For patients who report living and other situations that pose barriers to safe storage of a 4-week supply of medications, individual drug treatment centers will develop processes for providing GLE/PIB in quantities that can be safely stored by the participant.

At the treatment initiation visit, participants will be given a follow up appointment for 8 weeks after treatment initiation (expected end of treatment) with designated drug treatment center staff.

Standard of Care Referral to Offsite Location: Participants randomized to standard of care arm will be referred to an offsite HCV treatment site.

Using a signed release of medical information form, research staff will follow up with the referral site to see if the patient scheduled and subsequently attended an appointment and collect information on subsequent progress along the HCV care continuum.

If the patient is confirmed to have scheduled the appointment, study staff will contact the evaluating physician to make them aware that the study may provide GLE/PIB for HCV treatment.

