5.6 Follow-Up for Subject Withdrawal from Study

In order to minimize missing data for efficacy and safety assessments, subjects who prematurely discontinue study drug treatment should continue to be followed for all regularly scheduled visits, unless they have decided to discontinue the study participation entirely (withdrawal of informed consent). Subjects should be advised on the continued clinical importance of their data even if they discontinue treatment with study drug early.

If, during the course of study drug administration, the subject prematurely discontinues (D/C) study participation, the procedures outlined for the applicable Premature D/C Visit in the Schedule of Events

(Appendix A) should be completed. Ideally, this should occur on the day of study drug discontinuation, but no later than 2 days after their final dose of study drug and prior to the initiation of any other anti-HCV therapy. However, these procedures should not interfere with the initiation of any new treatments or therapeutic modalities that the investigator feels are necessary to treat the subject's condition. Following discontinuation of study drug, the subject will be treated in accordance with the investigator's best clinical judgment. All attempts must be made to determine the date of the last study drug dose and the primary reason for discontinuation of study drug or study participation. The last dose of any study drug and reason for discontinuation will be recorded in the eCRF.

If a subject is discontinued with an ongoing adverse event or an unresolved laboratory result that is significantly outside of the reference range, the investigator will attempt to provide follow-up until a satisfactory clinical resolution of the laboratory result or adverse event is achieved.

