6.2.2 Medical Complaints/Adverse Events and Serious Adverse Events

An AE is defined as any untoward medical occurrence in a subject or clinical investigation subject administered a pharmaceutical product and which does not necessarily have a causal relationship with this treatment. An AE can therefore be any unfavorable and unintended sign (including an abnormal

laboratory finding), symptom, or disease temporally associated with the use of a medicinal (investigational) product, whether or not the event is considered causally related to the use of the product.

An AE can result from use of the drug as stipulated in the protocol or labeling, as well as from accidental or intentional overdose, drug abuse, or drug withdrawal. Any worsening of a pre-existing condition or illness is considered an AE. Worsening in severity of a reported AE should be reported as a new AE. Laboratory abnormalities and changes in vital signs are considered to be AEs only if they result in discontinuation from the study, necessitate therapeutic medical intervention, meets protocol specific criteria (see Section 6.3 regarding toxicity management) and/or if the investigator considers them to be AEs.

Adverse event reporting will follow the requirements outlined below. Adverse events will also be recorded and tracked in a safety monitoring database by the investigators. Serious adverse events (SAEs) will be reported to the Institutional Review Board according to IRB guidelines and to AbbVie via the Johns Hopkins University Transplant Oncology and Infectious Diseases Clinical Research Center (TOID CRC).

All Grade 3 or higher and all SAEs related to the use of GLE/PIB in intervention arm or prescribed DAA course in SOC arm will be collected. Thus, AEs and SAEs will only be collected from the time of first DAA dose to 30 days after completion of DAA course.

All Grade 3 or higher AEs and all SAEs will be reviewed by the principal investigator as they occur in a timely manner. All AEs related or possibly related to GLE/PIB will be reported by the site to the TOID CRC within 72 hours of the site being made aware via the REDCap EDC system. All SAEs will be reported to the TOID CRC via the REDCap EDC system within 24 hours of the site being made aware. Notification of all SAEs will be made to AbbVie by the TOID CRC via email within 24 hours of entry into REDCap.

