APPENDIX A. SCHEDULE OF EVENTS (ALL PARTICIPANTS)

	Recruitment Screen	Day 0	Treatment Day 1	Treatment Week 4	End of Treatment -0d/+30d	Post-Treatment Week 12 -14d/+30d	Post-Treatment Week 24 -14d/+30d	Post-Treatment Week 36 -14d/+30d	Early D/C Visit
Eligibility Review ^a	X	X							
Vital Signs ^b		X							
Demographics		X							
Medical History		X							
Concomitant Medications ^c		X			X				
Randomization		X							
Referral to HCV Treatment (SOC Arm Only)		X							
AE/SAE Collection ^d			→	→	→				
Laboratory Testing									
HBsAg		X							
Pregnancy Test ^e		X							
CBC ^f		X							
HCV RNA ^g		X			X	X		X	X
CMP		X			X	X			X
Urine Toxicology Screen		X			X	X	X	X	
Dried Blood Spot		X			X	X	X	X	X
Surveys/Questionnaires									
Study Survey		X			X	X	X	X	
PRO/QOL Measures		X			X	X	X	X	
Intervention Arm Only									
Peer Contact ^h		X	→	→	→	→			X
Study Drug Dispensation ⁱ			X	X					

^aIncluding documentation of HCV infection (antibody) and treatment history.

^bIncluding height, weight, temperature, pulse, respiratory rate, and blood pressure.

^cAll medication (including supplements and over-the-counter) will be collected.

^dAE/SAE collection starts with initiation of DAAs, continues through 30 days after last DAA dose.

^eFor all participants of childbearing potential. Urine or serum test.

^fWith or without differential.

^gCLIA certified.

^hPeer contact to occur weekly and as needed between visits until SVR 12. Contact can be in-person, via phone, or video.

ⁱStudy drug can be dispensed in smaller amounts more frequently if participant is unable to maintain 4-week supply at home.

APPENDIX B. SCHEDULE OF EVENTS (PARTICIPANTS WHO DO NOT START HCV TREATMENT BY WEEK 12 AFTER RANDOMIZATION IN EITHER ARM)

For participants who have not initiated treatment by Week 12 after randomization, complete the following.

	Week 12 after randomization -14d/+30d	Week 24 after randomization -14d/+30d	Week 36 after randomization -14d/+30d	Week 56 after randomization -14d/+30d
Laboratory Testing				
Urine Toxicology Screen	X	X	X	X
Dried Blood Spot	X	X	X	X
HCV RNA ^e		X		X
Surveys/Questionnaires				
Study Survey	X	X	X	X
PRO/QOL Measures	X	X	X	X
Rescreen for SOC Participants to Rollover to Intervention Arm				
Eligibility Review		X		
Vital Signs ^a		X		
Concomitant Medications ^b		X		
HBsAg		X		
Pregnancy Test ^c		X		
CBC ^d		X		
CMP		X		
Peer Contact ^f		→		

^aIncluding height, weight, temperature, pulse, respiratory rate, and blood pressure.

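### Adverse events are to be collected to 30 days after the last dose, but Appendix A fixes no assessment at or after day 30, and in those days only the intervention arm has scheduled contact

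*Combined protocol and SAP*

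**What the plan says.** Section 6.2.2 sets the collection period: "Thus, AEs and SAEs will only be collected from the time of first DAA dose to 30 days after completion of DAA course". Footnote d to the AE/SAE row of Appendix A agrees with it.

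In Appendix A the AE/SAE row carries arrows at Treatment Day 1, Treatment Week 4 and End of Treatment. The last of these columns is headed "End of Treatment -0d/+30d". The next visit is "Post-Treatment Week 12 -14d/+30d", and its AE/SAE cell is empty. So is the cell for Early D/C, a visit that Section 5.6 wants ideally on the day the drug is stopped and "no later than 2 days after their final dose of study drug".

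On contact between visits, Section 4.2.9 says: "Peers will have a standard protocol for at least weekly phone contact with participants through post-treatment week 12". Appendix A lists peer contact under the intervention arm only. For the standard of care arm, Section 4.2.9 has research staff check with the referral site on appointments and progress in HCV care. It assigns no AE task.

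The arms are compared on this outcome. Exploratory endpoint 6 (Section 3.4) is the proportion with Grade 3 or higher AEs by arm. Section 7.3.3 calls the AE analysis mainly descriptive and adds Fisher's exact test between arms.

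**The concern.** The text promises a collection period that the schedule does not reliably close. If the End of Treatment visit takes place on time, nobody is scheduled to ask about events in the following 30 days. An event in that period is recorded only if the participant, a peer, the drug treatment program or the referral site brings it to the study's notice.

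Those informal routes are not equal. Intervention participants speak with a peer at least weekly throughout the period, and standard of care participants have no scheduled study contact in it. If contact prompts reporting, equal true rates could appear as more events under test and treat.

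Two features make this worth settling. Section 6.2.1 provides no data safety monitoring board, so oversight depends on what sites learn. Under Section 6.2.2 the 24-hour SAE reporting clock starts only when the site becomes aware.

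**Working it through.** No figure in the plan needs reproducing. The check is day arithmetic on the visit windows, with day 0 as the last dose.

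**Inputs.** Course length is 8 weeks for the study drug (Synopsis). Collection ends at day 30 (Section 6.2.2; Appendix A, footnote d). The End of Treatment window is -0/+30 days and the Post-Treatment Week 12 window is -14/+30 days (Appendix A). Peer contact is weekly (Section 4.2.9; Appendix A, footnote h).

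**Length of the collection period.** 8 × 7 + 30 = 86 days. The post-treatment part is 30/86 = 35%.

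**Days with no later scheduled AE assessment.** If the End of Treatment visit is on day v (0 ≤ v ≤ 30), the uncovered days are 30 − v. Whole weekly peer contacts in those days are (30 − v)/7, rounded down, and occur in the intervention arm only.

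| End of Treatment visit (day v) | Uncovered days | Weekly peer contacts, intervention | Scheduled study contacts, standard of care |
|---|---|---|---|
| 0 | 30 | 4 | 0 |
| 7 | 23 | 3 | 0 |
| 14 | 16 | 2 | 0 |
| 21 | 9 | 1 | 0 |
| 30 | 0 | 0 | 0 |

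Section 4.2.9 books the intervention arm's follow-up appointment for 8 weeks after treatment starts, the expected end of treatment. A visit kept as booked therefore sits at the top of the table. The section gives no corresponding appointment for the standard of care arm, so v could also differ by arm.

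**Next visit.** Post-Treatment Week 12 falls between 84 − 14 = day 70 and 84 + 30 = day 114. That is 70 − 30 = 40 to 114 − 30 = 84 days after collection closes. It could look back over the period, but its AE/SAE cell is blank.

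**Early D/C.** Section 5.6 separates two groups. Those who stop the drug but stay in the study keep their regular visits. Those who leave the study have the Early D/C visit, which may be the last chance to ask, and no AE mark is placed there.

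**Scope.** This arithmetic concerns Appendix A. Appendix B, for participants untreated at Week 12 after randomization, has no AE row.

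**The case against.** The other side has several good points.

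- A reader might infer that no visit covers the 30 days. That is not so. The End of Treatment visit carries AE collection and its window spans exactly those days; held on day 30, it leaves nothing uncovered. What stands is that no assessment is fixed at or after day 30.
- The AE row uses arrows, and footnote d makes collection continuous. The arrows at Treatment Day 1 and Week 4 also apply to all participants. This stands as to the obligation. It does not say who asks, or when, after End of Treatment.
- A reader might infer from weekly peer calls that capture does differ by arm, and count calls as a measure of it. The documents do not support that. Section 4.2.9 gives peers adherence and food-use surveys, with no AE questions. Both arms are recruited from programs they attend for ongoing care, and staff contact the referral site. Unequal capture is a risk of unknown size.
- A reader might infer that abnormal laboratory results at Post-Treatment Week 12 are lost because they fall after day 30. Section 6.2.3 still requires the investigator to evaluate Grade 3 and 4 laboratory abnormalities during the study. The 30-day limit is a stated design choice, and this point does not ask for it to be widened.
- The comparison is exploratory and mainly descriptive, the drug is used on label, and Section 6.2.2 confines collection to treatment-related events of Grade 3 or higher and SAEs. All of this limits the consequence.

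**Conclusion.** The text and the schedule do not fully match. Collection is promised to day 30 after the last dose, yet between 0 and 30 of those days have no later scheduled AE assessment, depending on the date of the End of Treatment visit. The upper limit is 30 of 86 days (35%). It assumes an 8-week course and a visit on the day of the last dose; a longer course in the standard of care arm would leave the 30 days unchanged and lower the share.

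Scheduled contact in those days is confined to the intervention arm. That is a reason to standardize how events are elicited. It does not show that the comparison is biased, and the documents give nothing from which to estimate the effect on exploratory endpoint 6. The primary endpoint is unaffected. The change is worth making because it is cheap and concerns safety data in a trial without a monitoring board.

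**What to change.** In Appendix A, mark AE/SAE collection at Early D/C and at Post-Treatment Week 12. At End of Treatment and Post-Treatment Week 12, ask the same structured question in both arms about the period from first dose to 30 days after the last dose. The 30-day limit itself stays as it is. In Section 7.3.3, base the between-arm comparison on these common assessments and list separately any event first reported through peer contact.

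The cost is amendment wording and one added form at visits that already exist in both arms. The drawback is recall: the Week 12 question is asked 70 to 114 days after the last dose, so it improves completeness but does not speed up awareness of SAEs. A brief contact near day 30, identical in both arms, would shorten recall and bring earlier awareness, at the price of one more contact per treated participant.

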6.2.3 Adverse Event Relationship to Study Drug

For the purpose of medical management, all Grade 3 and 4 AEs and laboratory abnormalities that occur during the study must be evaluated by the Investigator. All AEs and laboratory abnormalities deemed "clinically significant" based on the medical judgment of the Investigator will be managed and followed to a satisfactory clinical resolution.

The investigator will use the following definitions to assess the relationship of the adverse event to the use of study drug:

Reasonable Possibility – After consideration of factors including timing of the event, biologic plausibility, clinical judgment, and potential alternative causes, there is sufficient evidence (information) to suggest a causal relationship.

No Reasonable Possibility – After consideration of factors including timing of the event, biologic plausibility, clinical judgment, and potential alternative causes, there is insufficient evidence (information) to suggest a causal relationship.

6.2.4 Pregnancy

While not an AE, pregnancy in a study subject should be monitored. Information regarding a pregnancy occurring up to 30 days after end of treatment in a study subject and the outcome of the pregnancy will be collected.

In the event that a positive result is obtained on a pregnancy test for a subject or a subject reports becoming pregnant during the Treatment Period, the administration of study drug may be continued at the Principal Investigator's discretion after discussion with the subject, if the benefit of continuing study drug is felt to outweigh the potential risk. If a subject is discontinued, the subject will be monitored for SVR in the Post-Treatment Period.

6.3 Toxicity Management

The management of specific AEs and laboratory parameters is described below. This includes the following laboratory abnormalities:

If a subject experiences a post-baseline increase in alanine aminotransferase (ALT) to $> 3 \times$ upper limit of normal (ULN), which is also $> 2 \times$ baseline value, the subject, should have a confirmatory ALT measurement performed.

If, the ALT increase is confirmed to be $> 3 \times$ ULN, which is also $> 2 \times$ baseline value, the recommendations below, should be followed:

- Evaluate for alternate etiology of ALT elevation; document in the source, update the medical history and concomitant medications eCRF (if applicable), and obtain Anti-hepatitis A virus immunoglobulin M (HAV IgM), Anti-hepatitis A virus total (HAV Total), Anti-hepatitis B core (HBc) IgM, Anti-HBc Total, Anti-Hepatitis B surface (HBs), Hepatitis B Virus (HBV) DNA, HBsAg, Anti-hepatitis E virus immunoglobulin M (HEV IgM), Anti-hepatitis E virus immunoglobulin G (HEV IgG) and HEV RNA, and other additional tests, as appropriate.
- Manage the subject as medically appropriate.
- Repeat ALT, aspartate aminotransferase (AST), total and fractionated bilirubin, alkaline phosphatase and international normalized ratio (INR) within 1 week. Repeat liver chemistries as indicated until resolution.

Discontinue study drug if any of the following is observed at any time:

- ALT level is $\geq 3 \times$ ULN and total bilirubin of $> 2 \times$ ULN without initial findings of cholestasis (elevated serum alkaline phosphatase) in the absence of an alternate etiology including another drug capable of causing the observed injury.
- Increasing direct bilirubin or INR or onset of symptoms/signs of hepatitis.
- At the discretion of the investigator.

Alternate management of ALT increases is permitted with approval of the Sponsor Medical Director.

6.4 Product Complaint

A Product Complaint is any complaint related to the biologic or drug component of the product.

For a product this may include, but is not limited to, damaged/broken product or packaging, product appearance whose color/markings do not match the labeling, labeling discrepancies/inadequacies in the labeling/instructions (example: printing illegible), missing components/product, or packaging issues.

Product Complaints concerning the investigational product must be reported to the TOID CRC via the REDCap EDC system within 24 hours of the study site's knowledge of the event. Notification of product complaints will be made to AbbVie by the TOID CRC via email within 24 hours of the site reporting the complaint. Product Complaints occurring during the study will be followed up to a satisfactory conclusion.

7 STATISTICAL METHODS & DETERMINATION OF SAMPLE SIZE

7.1 Statistical and Analytical Plans

The primary analysis for the effectiveness of the test and treat strategy versus standard of care referral for HCV treatment initiation will be assessed using a logistic regression model and a two-sided Type 1 error rate (alpha) of 0.05. Since participants will be recruited from drug treatment programs at which they are receiving ongoing treatment for substance use disorder, we expect low rates of lost to follow up (10%).

7.2 Definition for Analysis Populations

All analyses will be conducted with a modified intention to treat approach, which excludes randomized participants who were found on testing to have an undetectable HCV RNA, HBsAg positive or a platelet count <150,000.

7.3 Statistical Analyses

7.3.1 Primary Analysis

Sample Size and Power Consideration Estimation

The planned sample size for the trial is 124 participants enrolled and randomized in a 1:1 ratio to test and treat strategy versus Standard of Care referral. This sample size is based on preliminary data from the CHAMPS study, which offered free onsite HCV treatment to HIV infected patients at an urban infectious disease clinic and achieved a 70% HCV treatment initiation rate.¹⁵ Data from community-based sites including the AIDS linked to the intravenous experience study suggest an HCV treatment start rate of 30% among community based people who use drugs enrolled in the oral DAA era in Baltimore²¹. Given differences in HCV treatment policies and restrictions, HCV treatment rates were estimated to be up to 55% in other cities prior to the COVID-19 pandemic. HCV treatment uptake rates reduced during and post-COVID 19. We estimate HCV treatment uptake between 30-50% in different cities, averaging 40%. Using these data points as estimates for treatment initiation in the test and treat arm (70%) and the treatment uptake in the referral arm (40%) power calculations are as follows. With a total sample size of 124 participants, we have 85% power at an alpha of 0.05 to detect a statistically significant difference in treatment initiation in the test and treat strategy versus the standard referral arm. The sample size of 124 allows for 110 completers should there be a ~10% drop out rate. If there is no drop out then the total enrollment of the HCV infected participants will be 124. We continue to expect that the treatment uptake will be 70% with the proposed test and treat interventions. Our proposed sample size of 55 completers per group (62 per group including possible drop outs) is adequate to distinguish between the hypothesized 70% uptake and the 40% non-intervention arm uptake with 85% power at the $p = 0.05$ threshold.

